For child participants, screening eligibility will be conducted via the adult participant. It is possible, given the definition of caregiver that is used, that the caregiver may not be able to answer specific questions regarding the child's inclusion criteria. If this is the case, the child's parent or legal guardian will be contacted to confirm the child's eligibility.

If a caregiver has more than 1 child in the eligible age range, the study team member conducting the screener will use a random number generator to select one child randomly, and assess the eligibility of this child. If the child is not eligible, then the next child's eligibility will be assessed. If the caregiver expresses a strong desire to assess the eligibility of a certain child in particular, then the study team member will be advised to start with the eligibility screening of this child.

Enrollment of the Intervention Arm

- Enrollment of adult participants (and child participants) in the intervention arm, after eligibility screening, completion of adult consent process and the child assent (with parent or legal guardian consent) process (Details regarding consent and assent as detailed in Sections 14-17 of the eIRB application).
- Any related enrollment processes related to the adult participant's participation in the DPP as routine care, will be conducted by the Brancati Center team as per routine practices for DPP enrollment.
- For the child, the enrollment form will confirm parent/legal guardian contact information (emergency contact information), the child's pediatrician, and food or other allergies to be aware of.

Randomization

- Participants will not be randomized to the intervention. All participants who are recruited for the intervention arm will be engaged in the FDPP intervention.

Recruitment and Screening Eligibility: Concurrent Control Group (Control Arm)

Recruitment of Concurrent Control Group (Control Arm):

The concurrent control group will consist of adults in the Brancati Center's DPP (who started the program within 6 months of the Intervention group) and who have children less than 18 years of age living in their household. We will recruit adult participants for the concurrent control groups through several means as detailed in "Section 13." This will include

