1) Recruitment from adults currently participating in Brancati Center DPP groups (which have started within 6 months of the Intervention Arm groups): During a DPP session, participants will be read a brief paragraph regarding the concurrent control group as follows and a flyer will also be distributed to group participants via email:

"There is a research study for DPP participants that you may be eligible for. This study involves adults in the DPP who have children less than 18 years living in their household. As part of the study, you would be asked to complete surveys once. The study team would also compare participants' DPP attendance and outcome data with that of other adult participants who are enrolled in a Family Diabetes Prevention Program pilot study. You would be compensated for your time."

If potential participants are interested, their contact information would be provided to the Family DPP study team; contact information of the study team would also be provided.

2) Recruitment from adults who are to start a Brancati Center DPP program: Individuals who are enrolled in (assigned to a DPP group, but not yet started) will be read the following during routine telephone calls conducted prior to group start:

"There is a research study for DPP participants that you may be eligible for. This study involves adults in the DPP who have children less than 18 years living in their household. As part of the study, you would be asked to complete surveys once. The study team would also compare participants' DPP attendance and outcome data with that of other adult participants who are enrolled in a Family Diabetes Prevention Program pilot study. You would be compensated for your time. Would you be interested in learning more about this study?"

Screening eligibility for the Concurrent Control Group (Control Arm)

Potential adult participants will be screened for eligibility for the concurrent control group by the study team via telephone.

Intervention Delivery (Family DPP)

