 - o **As per our Data Safety Monitoring Protocol** outlined in Section 32 of the IRB application, we will query participants about possible adverse events using the Adverse Events form at 6 and 12 month data collection points.

Data Collection for Concurrent Control Group (Control Arm)

- 1) Data collection associated with Routine Care (DPP protocol):
 - o **Adult-related outcomes:** Adult participants who are part of the Brancati Center's Diabetes Prevention will have data collected relevant to their participation in the program, as per the routine care protocol. This includes data collected as part of the DPP eligibility screening process and program enrollment process. During the program, this includes participants' attendance, weight (either measured if in-person visits, or self-reported) and self-reported physical activity minutes.
- 2) Additional data collection for concurrent control group: For adults in the concurrent control group, we will conduct a baseline survey. This survey will cover domains including: household demographics, child demographic information and household social

determinants of health. The survey may be conducted over telephone or via secure REDCap online link (self-administered).

3) Also, as per our **Data Safety Monitor Protocol** outline in Section 32 of the IRB application, we will query participants about possible adverse events using the Adverse Events form at 6 and 12 month time points via telephone.

b. If your study involves data/biospecimens from participants enrolled under other research studies with a written consent or under a waiver of consent, please list the IRB application numbers for those studies. Please note: Certificate of Confidentiality (CoC) protections applied to the data in source studies funded by NIH or CDC will extend to this new study if the funding was active in 2016. If this situation applies, Section 36, question 6 in the application will need to be answered “Yes” and “Hopkins Faculty” should be selected in question 7. No other documents are required.

For both the adult intervention arm participants and concurrent control group (control arm) participants, we will obtain adult participant attendance data, as well as weight and physical activity data, from the Brancati Center’s Diabetes Prevention Program participant database; these activities are undertaken under IRB protocol “IRB00179397: Evaluation of the Johns Hopkins Diabetes Prevention Program.”

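### Controls may be recruited from DPP groups already under way with no limit on consent time, so early dropouts are likely under-represented and control attendance may be raised in the exploratory FDPP-versus-DPP comparison.

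*Combined protocol and SAP*

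**What the plan says.** Section 3a, under recruitment of the control arm, gives two routes.

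- **Route 1:** "Recruitment from adults currently participating in Brancati Center DPP groups (which have started within 6 months of the Intervention Arm groups"). The approach is described as "During a DPP session, participants will be read a brief paragraph regarding the concurrent control group", and "a flyer will also be distributed to group participants via email".
- **Route 2:** people "assigned to a DPP group, but not yet started", approached in the routine calls before their group begins.

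The only time limit concerns program or group start. Section 3a describes controls as adults "who started the program within 6 months of the Intervention group", and the control criteria in Section 4 repeat the window for the group. Further detail is deferred: "We will recruit adult participants for the concurrent control groups through several means as detailed in" Section 13, which is not among these documents.

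Two statements bear on control entry without setting a deadline: "For adults in the concurrent control group, we will conduct a baseline survey", and "we will query participants about possible adverse events using the Adverse Events form at 6 and 12 month time points via telephone". Section 3c describes control participation as a single survey call.

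For the intervention arm, Section 3a has referred adults asked about the study once they have been found eligible for the DPP. For the other sources, the study team does that screening itself. Consent before the first session is a fair inference, but it is not stated.

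Section 3b takes attendance for both arms from the DPP database. Section 6a defines caregiver attendance as a percentage of sessions attended, and Section 6c analyses feasibility measures descriptively. Section 6c does not mention recruitment route or entry time.

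**The concern.** A person can hear the route 1 invitation only by still attending when it is read. The attendance record then counts sessions back to the start of the program, including weeks in which that person had, by selection, usually not dropped out. This is left truncation: those who left early are mostly missing from the control sample, while their counterparts in the FDPP arm are kept. Even if the two programs were identical, route 1 controls would show higher attendance than all DPP starters.

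Late entry is allowed. The window covers groups that began up to 6 months from the intervention groups, and Section 3f says the current control design came in by revision of the 4/20/22 protocol.

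At stake is a comparison that the Abstract gives as the reason for enrolling controls, and that Section 3f says will inform a larger FDPP-versus-DPP trial.

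**Working it through.** The plan has no figure to reproduce: it states no dropout rate, control sample size, route mix or consent timing. The following is an illustration.

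**Inputs**
- 33 sessions: midpoint of the 32 to 34 in Section 3a.
- 20 of them core: assumed (Section 3a says at least 16).
- Dropout 30% by 6 months and 50% by 12 months: assumed.
- 85% attendance while active: assumed.
- Identical programs, and all controls by route 1: assumed.

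**Retention.** The per-session hazard is constant within each period, and dropout occurs before a session.
- Core: h1 = 1 − 0.70^(1/20) = 0.0177
- Post-core: h2 = 1 − (0.50/0.70)^(1/13) = 0.0256
- S_j is the share still active at session j. The sum of S_j over 33 sessions is 24.30.

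**All starters:** 0.85 × 24.30 / 33 = 62.6% of sessions attended.

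**Adults present at session k:** A_k = [0.85(k − 1) + 1 + 0.85 × (sum of S_j for j > k) / S_k] / 33.

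At k = 8, S_8 = 0.867 and the later sum is 16.91. So A_8 = [5.95 + 1 + 16.58] / 33 = 71.3%, a gap of 71.3 − 62.6 = 8.7 points.

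**Dropouts joining at relative rate r** (for example through the emailed flyer): mean = [S_k·A_k + r(1 − S_k)·D_k] / [S_k + r(1 − S_k)], where D_k is the mean attendance of those who left before session k.

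At k = 8, D_8 = 8.8%. With r = 0.5 the mean is [0.867 × 71.3 + 0.0665 × 8.8] / 0.9335 = 66.8%, a gap of about 4.3 points (unrounded inputs).

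Control attendance minus all-starter attendance, in percentage points:

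| Entry session | r = 0 (upper bound) | r = 0.25 | r = 0.5 |
|---|---|---|---|
| 1 | 1.6 | 1.3 | 1.0 |
| 2 | 2.7 | 2.1 | 1.5 |
| 4 | 4.8 | 3.6 | 2.5 |
| 8 | 8.7 | 6.4 | 4.3 |
| 12 | 12.1 | 8.7 | 5.6 |

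About 0.4 point of each upper bound arises only because attendance at the invitation session is certain. The gaps scale with the route 1 share: half at 50%, none if all controls come by route 2.

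**Sensitivity.** With dropout from 20%/35% to 40%/60%, the upper bound is 1.2 to 3.3 points at sessions 1 to 2 and 8.5 to 15.8 at session 12. With 16 core sessions of 33, or 24 of 34, the session 8 figure is 10.5 or 7.5.

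**Opposing selection.** If dyad enrolment alone gave FDPP adults 20%/35% dropout, they would attend 69.9%, which is 69.9 − 62.6 = 7.3 points above DPP starters. Control minus FDPP, with all controls by route 1 and r = 0, would then be −4.6 at session 2, −2.5 at session 4, −0.5 at session 6, +1.4 at session 8 and +4.8 at session 12. With controls consented before start it would be −7.3.

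**The case against.** **The effect may be small.** Calling the control survey a baseline survey and planning a 6-month adverse-event query both point to early entry. The flyer can reach absentees, and route 2 is free of the problem. Entry at sessions 1 to 2, with half the controls by route 1 and dropouts joining at half rate, gives 0.5 to 0.8 point. Section 13 may contain a deadline. All of this stands, but none of it sets a limit in the documents at hand.

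**Separating the routes may not bring the comparison nearer the truth.** In the dyad-selection scenario above, pre-start controls sit further from zero than route 1 controls at every entry point tested. Session counts may also differ: FDPP adds 2 core sessions, and the documents do not settle whether the child-focused post-core sessions add to DPP sessions or replace them. With the 2 core sessions plus 4 or 8 added post-core sessions, and no dyad selection, the pre-start gap is +0.8 or +1.8 points. This stands as a limit on what the fix can claim. It does not justify keeping an avoidable bias in the hope that another one cancels it.

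**Entry time may be recoverable anyway.** Group start must be known to apply the control criteria, so a dated consent (assumed) would give weeks since start. A reader might infer that, without new fields, the effects could never be examined; the documents do not support that. Nor would recording route measure dyad selection.

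**A reader might extend the point to weight loss.** The documents do not support this. Section 6c states no imputation rule, and a complete-case version of the same model gives a gap of 0.0.

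**Conclusion.** The point holds as a modest weakness in an exploratory comparison. As written, route 1 can under-represent early dropouts and so raise control attendance. Under the stated assumptions, the upper bound is about 2 to 3 points for entry at sessions 1 to 2, 9 at session 8 and 12 at session 12. If dropouts join at half the attenders' rate, it is about 1 to 1.5, 4 and 6. All these figures shrink with the share recruited by route 2. They rest on assumed dropout, attendance, entry session and route mix, because the documents supply none of these.

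A reader might conclude that the comparison is tilted against the FDPP overall. That does not follow: dyad enrolment, with three data collections, may select committed FDPP adults and push the other way. A reader might also think the primary objective is compromised. It is not, because the FDPP process measures describe one arm and do not use the controls. Confidence is medium, mainly because Section 13 is not available.

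**What to change.** 1. At control consent, record the recruitment route and the weeks since the participant's group started.
2. In Section 6c, show the between-arm attendance comparison for controls consented before their group's first session separately from route 1 controls, alongside the pooled comparison.
3. State that remaining differences may still reflect dyad selection and any difference in the number of sessions offered.
4. If few controls consent before start, keep the pooled comparison descriptive and state the limitation.

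If Section 13 already sets an early consent deadline, a sentence quoting it in Section 3a would largely settle the point.

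The cost is two short fields and a few sentences in Section 6c. The downside is smaller control strata, hence less precision in a pilot whose size is set mainly by budget and recruitment experience, and slightly more analysis. Neither recruitment route has to be dropped.

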- Delivery of the CDC-certified Prevent T2 curriculum, with additional CDC- approved modifications, with a total of 32-34 sessions delivered over a 12-month period. In the initial “core” period (first 6 months), there are at least 16 sessions delivered on a weekly basis. In the “post-core” period, additional (at least 6) sessions are offered over a 6 month period.
- The sessions are group-based, and led by a CDC-certified lifestyle intervention coach. Sessions are delivered either in-person, at community-partner sites or on the JH campus, or via a virtual synchronous platform (Zoom).
- The Brancati Center follows all CDC guidelines (<https://www.cdc.gov/diabetes/prevention/pdf/dprp-standards.pdf>) with regards to program content and data collection. Baseline data collection includes demographics relevant to the program. Throughout the program, data are collected on participants' weight, minutes of physical activity, self-monitoring of diet, and attendance. These data are currently maintained in a secure, RedCAP database.
- In addition to delivery of the evidence-based, CDC recommended curriculum, the Brancati Center team has identified and implemented several strategies to address both long-term engagement and barriers to weight loss and dietary modification. These include:
 - o For engagement:
 - o Providing participants with Progress Charts that show their individual weight loss, the average weight loss of their group, and how their group's weight loss compares to other groups
 - o Offering activities outside of the regularly scheduled group (e.g., informational sessions)

- Engagement campaigns (e.g., “Spring into Summer”) where participants receive small incentives (e.g., gift cards, healthy snacks, exercise equipment) for attendance, self-monitoring, and being physically active
- Raffles
- Guest speakers
- For barriers related to weight loss and self-monitoring:
 - Grocery store tours
 - One-on-one nutrition counseling from a registered dietitian
 - Providing sample recipes and food items to trial

2) Adult participants will be engaged in the Family-Oriented Diabetes Prevention Program (FDPP). There may be non-study participants (other Brancati Center DP participants) also participating in the group (as DPP participants).

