- The Family DPP intervention itself will be delivered as per routine care practices of the Johns Hopkins Brancati Center's Diabetes Prevention Program. Currently, the program is being delivered via a distance-learning modality (Zoom) to participants, in the setting of the COVID-19 pandemic. Thus, we anticipate that participants will receive the Family DPP in a distance-learning format; there may be the possibility of certain sessions held in-person either at our community partner site or in a conference room of appropriate size on the Johns Hopkins East Baltimore medical campus. We will at the minimum follow Johns Hopkins related guidance regarding in-person gathering size restrictions and other precautions (physical distancing, masks).

- If the enrolled adult study participant is not the parent or legal guardian of the child for whom they identified as a caregiver as per our eligibility definition, then we will request the parent or legal guardian to complete a permission slip for the child's attendance to any session or study visit (uploaded in the eIRB application, Supplementary Materials).

Data Collection for Intervention Arm

- 1) Data collection associated with Routine Care (DPP protocol):
 - o **Adult-related outcomes:** Adult participants who are part of the Brancati Center's Diabetes Prevention Programs (in this scenario, this will include those adults who are receiving Family DPP as well), will have data collected relevant to their participation in the program, as per the routine care protocol. This includes data collected as part of the DPP eligibility screening process and program

enrollment process. During the program, this includes participants' attendance, weight (either measured if in-person visits, or self-reported) and self-reported physical activity minutes.

- 2) Data collection associated with the study:
 - o Survey instruments are included in the Supplementary Materials section of this eIRB application.

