 - a. Caregiver (adult participant) knowledge and attitudes towards healthy-related behaviors
 - b. Perceived self-efficacy for behavioral change
 - c. Parenting self-efficacy for behavioral change
 - d. Family Home Environment
2. Caregiver (adult participant) Health behaviors and health outcomes
 - a. Physical activity- total minutes of moderate/vigorous physical activity in weeks preceding and whether caregiver meets DPP physical activity goal of 150 minutes/week of moderate-vigorous physical activity; and dietary
 - b. Dietary patterns

- c. Percent weight loss from baseline
- 3. Child health behavior and health outcomes
 - a. Physical activity- minutes/day
 - b. Screen time (hours/day)
 - c. Fruit and vegetable intake
 - d. Sugary beverage intake
 - e. Sleep duration and sleep behaviors
 - f. BMI z-score change
- c. Statistical plan including sample size justification and interim data analysis.

As the main objective of this study is evaluating FDPP feasibility and acceptability measures, sample size is primarily informed by budgetary constraints and our experience recruiting individuals for the DPP as well as recruitment for the study thus far.

Feasibility, acceptability and fidelity measures will be analyzed with descriptive statistics (Table 2). Intervention targets will be analyzed as continuous variables (means or numerical scores). Caregiver and child health behaviors will be analyzed as continuous variables (average value/day) and a binary variable (achievement of goal). The caregiver health outcome will be modeled as a continuous variable (percent of weight loss from baseline) and binary variable (achievement of 5% weight loss goal). The child health outcome is the BMI Z-score, a continuous variable. Within-groups, we will use 1) paired-t tests to analyze pre-post changes (from baseline to 6 months and baseline to 12 months) of continuous variables; and 2) McNemar's exact test to examine pre-post changes in proportion achieving behavioral and outcome goals (binary variables). Between groups, we will use 1) 2-sample t-tests to compare the magnitude of mean group change in values of continuous variables; and 2) Fisher's exact test to compare proportion achieving goals at 6 and 12 months. If continuous variables do not meet distribution assumptions necessary for use of parametric tests (t-tests), we will use appropriate non-parametric tests (Mann-Whitney test or, for paired data, Wilcoxon signed-rank test).

- d. Early stopping rules.

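### Percent weight loss is analysed without regard to whether each adult weight was measured or self-reported, so a participant whose mode changes between baseline and follow-up contributes a false weight change

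*Combined protocol and SAP*

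**What the plan says.** **Source of the weights.** In Section 3.a, the data collection text for the intervention arm and for the concurrent control group uses the same rule: "weight (either measured if in-person visits, or self-reported". Section 3.b confirms that both arms draw on the routine programme database: "we will obtain adult participant attendance data, as well as weight and physical activity data". No separate study weigh-in of adults is described. Child height and weight, by contrast, must be taken in person.

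**Delivery format.** The intervention description in Section 3.a allows sessions in person or by Zoom. For the intervention arm, Section 3.a (Intervention Delivery) says "we anticipate that participants will receive the Family DPP in a distance-learning format", and adds that "there may be the possibility of certain sessions held in-person". Controls are adults in separate groups of the same programme, "who started the program within 6 months of the Intervention group".

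**Analysis.** Section 6.c models the caregiver outcome as "percent of weight loss from baseline" and as achievement of the 5% goal. Changes from baseline to 6 and to 12 months are tested within arms by paired t-tests and between arms by two-sample t-tests. Binary goals are tested by McNemar's and Fisher's exact tests, and rank tests replace the t-tests where distributions require. The text does not say whether mode is recorded, whether baseline and follow-up must share a mode, which weight counts as the 6- or 12-month value, or whether any analysis takes mode into account.

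**The concern.** A change score assumes that both weights were obtained in the same way. Suppose self-report runs below scale weight. A self-reported baseline followed by a measured follow-up then hides real loss, and the reverse order creates loss that did not happen. None of the planned tests can separate this from true change.

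Two results are exposed. The within-arm change is biased whenever switches run mainly in one direction, even if both arms switch equally. The comparison between arms is biased only if net switching differs between them. Section 3.f says the comparison is meant to inform a larger trial of the family programme against the standard one, so an artefact of format could carry into that trial's planning.

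**Working it through.** The documents give no sample size, SD, expected weight loss or self-report error, so there is no stated figure to reproduce. What follows is an illustration on assumed inputs.

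**Inputs**
- From the documents: the mixed weight rule in both arms (3.a), the 5% goal and the planned tests (6.c), and non-randomised allocation (3.a).
- Assumed: the gap between self-reported and measured weight, *b*, is 0.5 to 2 kg; baseline weight, *W*, is 80 to 100 kg; for the 5% goal, true mean loss is 4% with SD 5 points, normally distributed.

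**Step 1: false change per switcher**, approximately 100 × *b* / *W* percentage points.
- Smallest: 100 × 0.5 / 100 = 0.5
- Largest: 100 × 2 / 80 = 2.5

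The sign depends on the direction of the switch.

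**Step 2: within-arm bias** = net share switching × Step 1. With an assumed 30% switching one way, this is 0.30 × 0.5 = 0.15 to 0.30 × 2.5 = 0.75 points.

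**Step 3: bias in the arm difference** = (net share in the family arm − net share in control) × Step 1.
- 50% against 10%: 0.40 × 0.5 = 0.2 to 0.40 × 2.5 = 1.0 points
- 30% against 30%, same direction: 0
- Nobody switches: 0

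All these shares are assumed.

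**Step 4: the 5% goal.** With mean 4 and SD 5, P(loss ≥ 5) = 1 − Φ(0.2) = 42.1%. If everyone's recorded loss shifts by 1 point:
- upward (mean 5): 50.0%
- downward (mean 3): 34.5%

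If 30% of an arm shift upward by 1 point, the share at goal moves by about 0.30 × (50.0 − 42.1) = 2.4 percentage points.

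**Step 5: does pairing by mode remove it?** With a constant offset, two self-reported weights give a recorded loss of true loss × *W* / (*W* − *b*). In the worst case above, a true 4% becomes 4 × 80 / 78 = 4.10%, an error of 0.1 point against 2.5 for a switch. The offset largely cancels.

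**The case against.** The strongest reply is that the scenario the protocol expects contains almost no switching. The family programme is anticipated on Zoom, so weights would be self-reported throughout. This stands: in that case only ordinary self-report error remains.

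A reader might infer that delivery was already moving between formats. The documents do not say so. They describe current Zoom delivery and leave in-person sessions as a possibility.

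A reader might also infer that the arms will differ in switching. Separate groups, the six-month start window and the lack of randomisation allow this, but nothing shows it. The weight rule, database and centre are the same for both arms. Nor does the in-person child measurement establish it, because no adult weigh-in is described at that contact and adult weights come from the programme database.

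It is also fair that mode may be handled in material not reproduced here. Section 3.a says the centre follows CDC data collection guidance, and Section 3.b refers to a separate IRB protocol for the database. The supportable statement is that this plan does not address mode, not that mode goes unrecorded.

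Finally, the kilogram offset and the switching shares are assumptions, and the outcome is secondary in a feasibility pilot. Both points limit the importance. Neither removes the gap in Section 6.c.

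**Conclusion.** The concern holds conditionally. Section 3.a permits two kinds of adult weight, and Section 6.c treats them as one. If any participants change mode between baseline and follow-up, that change is counted as weight change.

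Under the assumed offset and body weights, the size is 0.5 to 2.5 percentage points per switcher. The upper end is half the 5% goal, but it applies to one switcher at the extreme of both ranges and should not be read as the bias in an arm mean or in the arm difference. The arm-level effect is scaled by the difference in net switching, and is zero if shares and directions match. Whether any switching will occur, and whether it will differ by arm, cannot be determined from the documents.

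Importance is low to moderate. The feasibility, acceptability and fidelity outcomes are untouched. The case for acting is that the safeguard is cheap.

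**What to change.** 1. Extract the mode (measured or self-reported) with each adult weight taken from the programme database. If the field is absent, derive it from the format of the session at which the weight was recorded, using the rule already in Section 3.a.
2. Tabulate mode by arm at baseline, 6 and 12 months, with the number of participants whose mode changes and in which direction.
3. If any participants switch, add to Section 6.c a pre-specified sensitivity analysis of percent weight loss and the 5% goal, restricted to baseline and follow-up weights of the same mode within a fixed window around each time point. Use the tests already planned. A regression term for mode is not suitable, because the plan has no regression model.

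Keep this as a sensitivity analysis and do not let it replace the main one. Participants without a same-mode pair drop out of it. They may be more than a few, and losing them could introduce selection in an already non-randomised comparison.

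The cost is one field in the data extract, which the database may or may not already hold, one table and a few sentences in Section 6.c. No new measurements are needed. If nobody switches, the table alone settles the point.

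### The t-tests on 6- and 12-month weight change use, on their natural reading, only adults weighed at those times; dropout related to weight loss can bias them, while repeated program weights go unused

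*Combined protocol and SAP*

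**What the plan says.** Section 6.b lists percent weight loss among the secondary outcomes. Section 6.c says it will be "modeled as a continuous variable (percent of weight loss from baseline) and binary variable (achievement of 5% weight loss goal"). The tests for continuous outcomes are "paired-t tests to analyze pre-post changes (from baseline to 6 months and baseline to 12 months) of continuous variables" within groups and "2-sample t-tests to compare the magnitude of mean group change in values of continuous variables" between groups. For goals, the between-group test is "Fisher's exact test to compare proportion achieving goals at 6 and 12 months". If distributional assumptions fail, "we will use appropriate non-parametric tests (Mann-Whitney test or, for paired data, Wilcoxon signed-rank test").

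Section 6.c gives no missing-data rule, analysis population, window for the 6- or 12-month weight, sensitivity analysis, sample size, SD or dropout rate. Section 3.h foresees that some people will end participation early.

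On the data side, the description of the DPP in Section 3.a states: "Throughout the program, data are collected on participants' weight, minutes of physical activity, self-monitoring of diet, and attendance". The data-collection parts of Section 3.a repeat this for each arm and add that weight is either measured in person or self-reported. Section 3.b says of both arms that "we will obtain adult participant attendance data, as well as weight and physical activity data" from the program database.

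**The concern.** A change score needs both of its values. An adult with a baseline weight and several program weights, but none at month 12, contributes nothing to a 12-month t-test. The rank-test fallback does not help: it is triggered by the shape of the distribution and drops the same people. If those who stop differ in weight loss from those who stay, the mean loss and the 5%-goal rate describe those who stayed.

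The comparison of arms is exposed as well. Under Sections 3.c and 8, intervention adults have three study visits, each paid $50. Controls have one survey, paid $30. Controls are also telephoned about adverse events at 6 and 12 months, but no weight collection is stated for that call. Missing weights could therefore plausibly differ by arm, and attendance is itself one of the quantities to be compared. Section 3.f says the comparison is meant to inform a larger comparative effectiveness trial, so a distorted estimate could carry into that design.

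**Working it through.** The plan states no figure to reproduce. Every number below rests on assumed inputs and shows scale only. Weight loss is written as a positive percentage.

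**1. Bias within one arm.** Let d be the dropout proportion, rho the correlation between weight loss and the tendency to stay, and z the standard normal quantile of d. Under normal selection, bias in the completer mean = rho × SD × phi(z) / (1 − d). With SD 5 and rho 0.3 (both assumed):

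- d = 0.20: phi(z) = 0.280, so 0.3 × 5 × 0.280 / 0.80 = 0.52 points.
- d = 0.40: phi(z) = 0.386, so 0.3 × 5 × 0.386 / 0.60 = 0.97 points.

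| rho | 20% dropout | 40% dropout |
|---|---|---|
| −0.3 | −0.52 | −0.97 |
| 0 | 0 | 0 |
| 0.1 | +0.17 | +0.32 |
| 0.3 | +0.52 | +0.97 |
| 0.5 | +0.87 | +1.61 |

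**2. Bias in FDPP minus DPP**, with rho 0.3 in both arms, is the difference of the two arm biases. With 30% dropout in each arm it is 0.00. With 20% in FDPP and 40% in DPP it is −0.44. With 40% and 20% it is +0.44.

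**3. What the recorded weights can recover.** Simulation with 200,000 people per scenario: weights at months 1 to 6, 8, 10 and 12; true mean loss 4% at both 6 and 12 months; dropout at each occasion depending on weight loss, with log-odds 0.15 or 0.30 per percentage point where a relation is assumed. The all-weights estimate is a normal-likelihood estimate with a separate mean at each occasion. Results at month 12 (true mean 3.99 to 4.00):

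| Dropout depends on | Dropout by month 12 | Completers | All weights |
|---|---|---|---|
| nothing | 27% | 3.99 to 4.00 | 4.00 |
| last recorded weight, poorer losers leave | 29% to 34% | 4.60 to 5.26 | 3.99 to 4.00 |
| unseen current weight, poorer losers leave | 29% to 35% | 4.71 to 5.47 | 4.12 to 4.26 |
| better losers leave (0.15) | 29% | 3.30 to 3.40 | 3.89 to 3.99 |

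Using all weights removes the bias when recorded weights explain dropout, and most of it when they do not.

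**4. The 5% goal.** With dropout on the last recorded weight at log-odds 0.15 (29% dropout), the true rate is 42%. Completers give 46%. Counting missing weights as not achieved gives 33% (0.46 × 0.71). The plan does not say which would be reported.

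**5. Why time must not be a single straight line.** Suppose the true change is −4% × min(t/6, 1), a plateau after month 6, with monthly weights at t = 0 to 12 and no dropout. The mean is −4 × 9.5/13 = −2.92, the mean of t is 6, and the sum of squares of t is 182. The cross-product is −4 × (21 − 35/6) = −60.7, so the slope is −60.7/182 = −0.333 per month. The fitted line gives −2.9% at month 6 and −2.92 − 6 × 0.333 = −4.9% at month 12, against a true −4% at both.

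**The case against.** The strongest reply is that the completer rule is inferred. Section 6.c does not say that dropouts are excluded and does not define the two weights; a last recorded weight would also fit the text. Section 7 calls for a report of adult percent weight change at 6 and 12 months in the intervention arm, and weights may be self-reported, so losing contact with sessions need not mean losing the weight. That stands, and is why the point is put as the natural reading and why the fix starts with a definition.

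A reader might infer that dropout will inflate weight loss. The documents do not support that. They say nothing on who stops attending, and the bias is zero if dropout is unrelated to loss and downward if better losers leave. Nor do they establish a weight at each of the 32-34 sessions: the text says only that weights are collected during the program.

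A reader might also want one model with a random linear slope for every outcome. Step 5 shows that a straight line can mislead even with complete data. Arm terms cannot be estimated for survey scores or BMI z-score, because controls give one baseline survey on demographics and social determinants and no child measures.

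Finally, this is a secondary outcome in a non-randomized pilot whose primary measures are descriptive. At SD 5 the standard error of one arm's mean is 5/√15 = 1.3 points with 15 people and 5/√30 = 0.9 with 30, so sampling error may exceed the bias at 20% dropout. That limits the severity. It does not justify leaving available data unused.

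**Conclusion.** The concern holds in conditional form. As naturally read, the stated tests use only adults with a 6- or 12-month weight, although further weights are obtained for both arms; a better method is available from data already in hand. Bias arises only if dropout is related to weight loss, and its sign within an arm follows that relation. Between arms it also depends on how dropout differs, and may be zero or of either sign. The illustrative size, about 0.5 points at 20% dropout and 1.0 at 40%, rests on an assumed SD of 5 and correlation of 0.3, neither of which is in the documents. Severity is low to moderate.

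**What to change.** For adult weight, amend Section 6.c to:

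- define the 6- and 12-month weight windows;
- estimate change at both times from a mixed model for repeated measures on all recorded weights from all enrolled adults, with arm, time and arm-by-time, time being categorical (or a spline or piecewise term with a knot at 6 months, not a single linear slope);
- name a simpler covariance structure as the fallback if the sample is small;
- report the number with missing weights by arm;
- give the 5% goal over all enrolled adults beside the observed-case figure, saying how a missing weight counts.

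Any repeated-measures model for survey scores or BMI z-score should be for the intervention arm only, without arm terms.

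The cost is plan wording and modest programming, with no new data collection. The model assumes that earlier recorded weights explain dropout; where they do not, step 3 leaves a residual of about 0.1 to 0.3 points. It also does not repair the selection of controls from people already attending DPP groups (Section 3.a, control recruitment), which should be stated as a separate limitation.
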